9.0 DRUG INFORMATION

9.1 Indocyanine green: Indocyanine Green has FDA approval for determining hepatic function and liver blood flow. Please refer to the Package Insert for complete details.

9.2 Description: IC-GREEN™ is a sterile, lyophilized green powder containing 25 mg of indocyanine green with no more than 5% sodium iodide. It is packaged with Aqueous Solvent consisting of Sterile Water for Injection used to dissolve the indocyanine green. IC-GREEN™ is to be administered intravenously. Indocyanine green is a water soluble, tricarbocyanine dye with a peak spectral absorption at 800 nm. The chemical name for Indocyanine Green is 1-H-Benz[e]indolium,2-[7-[1,3-dihydro-1,1-dimethyl-3-(4-sulfobutyl)-2H-benz[e]indol-2-ylidene]-1,3,5-heptatrienyl]-1,1-dimethyl-3-(4-sulfobutyl)-hydroxide, inner salt, sodium salt. IC-GREEN™ has a pH of approximately 6.5 when reconstituted. Each vial of IC-GREEN™ contains 25 mg of indocyanine green as a sterile lyophilized powder.

9.3 Side effects: Anaphylactic or urticarial reactions have been reported in patients with or without history of allergy to iodides. If such reactions occur, treatment with the appropriate agents, e.g., epinephrine, antihistamines, and corticosteroids should be administered. See package insert for comprehensive list of adverse events.

9.4 Drug Interactions: No interactions with patient medications. Heparin preparations containing sodium bisulfite reduce the absorption peak of IC-GREEN™ in blood and, therefore, should not be used as an anticoagulant for the collection of samples for analysis.

9.5 Preparation and Dispensing: Under sterile conditions, the IC-GREEN™ powder should be dissolved with the Aqueous Solvent provided for this product, and the solution used within 6 hours after it is prepared. If a precipitate is present, discard the solution. The amount of solvent to be used can be calculated from the dosage form which follows. It is recommended that the syringe used for injection of the dye be rinsed with this diluent. Isotonic saline should be used to flush the residual dye from the cardiac catheter into the circulation so as to avoid hemolysis. With the exception of the rinsing of the dye injection syringe, saline is used in all other parts of the catheterization procedure.

9.6 Administration for patients indicated to receive IC-Green from the treating physician:

- 9.6.1 IC-GREEN testing will be administered according to the study calendar.
- 9.6.2 The patient will be studied in a fasting state. Patients should not eat 4 hours prior to the test. Coffee and/or water are allowed up to approximately two hours before the test. Patients should take all of their medications as usual. The patient will be weighed and the dosage calculated on the basis of a recommended 0.5 mg/kg of body weight. The dose given must be within 20% of the total recommended dose. There will be approximately a 6 cc blood draw followed by rapid IV push of the IC-GREEN at time 0. Following I.V. administration via catheter, serum samples will be collected at approximately 5, 10, 15 and 20 minutes after injecting the dye. Each blood draw will be approximately 6 cc. The patient will have two different catheters one will be used for the IC-GREEN infusion, and the other catheter will be used to draw the samples. The catheter will be flushed with saline following each blood draw.
- 9.6.3 The IC-GREEN test will be administered by trained personnel in the Michigan Clinical Research Unit "MCRU". The dye is commercially available and will be ordered from UMHS pharmacy (formulary). Radiographic contrast agents are administered routinely in the department and it is fully equipped to treat an anaphylactic reaction, should one occur.

10.0 CORRELATIVES/SPECIAL STUDIES

The goal of the planned correlative studies is to collect data on plasma biomarkers of treatment efficacy, toxicity, and liver function to plan further enhancements to individualized RT.

10.1 Sample Collection Guidelines

10.1.1 Blood and urine sample collection and processing

- 10.1.1.1: Collection of approximately 30-50 mls of blood will be performed by venipuncture at the specified time points. When possible, blood collection will be coordinated with other routine blood studies. These blood samples will be drawn at the clinical blood drawing station in the Radiation Oncology department at UH or at the Michigan Clinical Research Unit (MCRU).
- 10.1.1.2 Blood Specimen Processing: Whole blood will be obtained by venipuncture at each time point and will be processed at Michigan Clinical Research Unit (MCRU) specimen core and processing laboratory. Blood Samples will be labeled with the subject's coded study number and collection date.

The processing will happen as described in the current SOP of the Biorepository.

10.1.1.3 Subjects will provide approximately 20-40 ml of urine at the specified time points, if able.

10.1.1.4 Urine Processing: The urine samples will be processed at the MCRU specimen core and processing laboratory. A maximum of 20 2-ml aliquot tubes will be filled at each collection.

10.1.2 Biopsy collection and processing:

10.1.2.1 For patients who will undergo standard of care percutaneous fiducial placement at the University of Michigan for radiation targeting, they will optionally also consent to undergo percutaneous tumor biopsy during the same procedure. 2-3 18G cores will be obtained following routine clinical practice.

10.1.2.2 Biopsy Specimen Processing: Depending on sample abundance, the cores will be processed for RNA, DNA, and protein extraction, as well as standard histology. For RNA, the cores will be placed into an eppendorf tube and the sample covered with RNAlater completely. It will be stored in a 4 degree refrigerator for 24 hours, then transferred to a -80 degree freezer for later extraction. For frozen section, part of the sample will be placed into a plastic mold, and the sample covered with OCT compound completely, and then stored in -80 degree freezer immediately. A separate piece of tissue will be snap frozen at -80 degree freezer separately for later DNA and protein extraction. Standard methods for formalin-fixed paraffin embedding will be followed.

10.2 Specimen Banking

Blood and urine specimens not immediately utilized for plasma biomarkers will be stored for future biomarker analysis, as we anticipate advancement in experimental technology and preliminary results. Other techniques and tests also will be applied if they are found to be superior.

10.3 Virtual radiotherapy planning

CTs and MRIs obtained as part of this study will be coded and the information used for further advancements to treatment planning, including deformable registration and dose accumulation.

11.0 STATISTICAL CONSIDERATIONS

11.1 Study Design

This is a pilot study of individualized adaptive RT, which consists of 3/5 of a planned total course of treatment, a one month break, assessment of global and spatial liver function change using IC-Green or ALBI, and perfusion MRI, and the remainder of treatment adjusted for global and spatial changes in liver function. The primary endpoints are to establish the feasibility of this approach and to obtain preliminary estimates of safety and efficacy both overall and as they relate to treatment and patient characteristics. At the completion of this trial we will have the necessary data to define a SBRT treatment approach that is individualized and adaptive and ready to be compared to standard SBRT in a randomized trial.

Patients will have an initial plan with total dose chosen such that the estimated probability of toxicity (increase in CP of 2 points or more within 6 months of RT) from the first three of five planned treatments is at most 10%. In order to protect the safety of individual patients, after delivering 60% of the planned total treatment, there will be a 1 month break at the end of which, ALBI or ICG will be measured again and a new treatment plan will be developed.

This last course of treatment may be adapted (relative to the first course) globally in one of 2 ways. First, if there is no remaining enhancement on the MRI scan, no further radiation will be given because the tumor is likely to be cured. The second possible adaptation is intended

to prevent clinically significant decline in liver function in patients whose livers appear to be sensitive to RT. Child-Pugh (CP) score is a standard measure of liver function, and an increase of 2 points or more on this scale is considered clinically significant. Early changes in ICG retention and ALBI reveal subclinical changes in liver function that predict later liver toxicity, assessed by a change of 2 in CP score 6 months after treatment.

Maximizing tumor control and minimizing liver toxicity are competing objectives when selecting RT dose for these patients. To make this tradeoff explicit and quantitative, the dose during the second course of treatment will be selected as the minimum of

- 1) The dose that maximizes $\text{Prob}(\text{Local Control at 1 year}) - 4 * \text{P}(\text{Toxicity})$
- 2) The dose associated with a 25% estimated risk of toxicity.

That is, additional dose is deemed to be beneficial if the increase in local control is at least 4 times greater than the increase in toxicity. The key advantage of this approach over an isotoxic approach is that patients are exposed to risk of toxicity in direct proportion to their benefit in terms of increased local control. Thus patients are not unnecessarily exposed to higher rates of toxicity (e.g. 20%) unless the improvement in expected local control is large enough. Similarly, patients are not constrained to an arbitrary rate of toxicity (e.g. 15 or 20%) if allowing the rate of toxicity to exceed this threshold results in a large enough increase in local control. At the same time we still place a hard upper limit of 25% on the risk of toxicity to any patient. The overall rate of toxicity in this population of patients is expected to be lower than 25%.

In the above, toxicity is defined as increase in CP of 2 points or more within 6 months of RT and local control is defined as absence of tumor progression within 1 year of treatment. For purposes of this dose selection, local control will be estimated from a simple Cox model as a function of tumor dose while the toxicity model will include the change in ICGR15 at the mid-treatment timepoint.

The decision to continue treating patients with further radiation is based on analysis of the information from the ICG results or ALBI, and not RECIST measurements. These measurements are recommended and are not required to determine patients' coming off-study treatment or study protocol. In addition, baseline measurements are not needed at the time of enrollment.

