12.0 DATA AND SAFETY MONITORING	26
13.0 QUALITY ASSURANCE AND AUDITS	27
14.0 REFERENCES	28
15.0 APPENDIX	30

ABBREVIATIONS

AE	Adverse Event
ALB	Albumin
ALT	Alanine Aminotransferase
AST	Aspartate Aminotransferase
BUN	Blood Urea Nitrogen
CBC	Complete Blood Count
CMP	Comprehensive Metabolic Panel
CP	Child Pugh
CR	Complete Response
CT	Computed Tomography
CTCAE	Common Terminology Criteria for Adverse Events
CTO	Clinical Trials Office
DLT	Dose Limiting Toxicity
DSMB	Data and Safety Monitoring Board
DSMC	Data and Safety Monitoring Committee
DSMR	Data and Safety Monitoring Report
GTV	Gross Tumor Volume
H&P	History & Physical Exam
HRPP	Human Research Protections Program
IRB	Institutional Review Board
IV (or iv)	Intravenously
MTD	Maximum Tolerated Dose
NTCP	Normal Tissue Complication Probability
OS	Overall Survival
PD	Progressive Disease
PFS	Progression Free Survival
PI	Principal Investigator
PR	Partial Response
PRC	Protocol Review Committee
PTV	Planning Target Volume
QOL	Quality of Life
RT	Radiotherapy
SAE	Serious Adverse Event
SBRT	Stereotactic Body Radiotherapy
SD	Stable Disease
TBILI	Total Bilirubin
UaP	Unanticipated Problem
UMCCC	University of Michigan Comprehensive Cancer Center
WBC	White Blood Cells

STUDY SCHEMA

STUDY SYNOPSIS

Title	A Pilot Study of Individualized Adaptive Radiation Therapy for Intrahepatic Cancer
Methodology	Single arm
Study Duration	2 years
Study Center(s)	Single-center
Objectives	Determine the safety and efficacy of individualized adaptive radiation therapy for intrahepatic cancer
Number of Subjects	80 evaluable patients
Inclusion Criteria	Patients who have hepatocellular carcinoma
Exclusion Criteria	Patients who have a known allergy to intravenous iodinated contrast agents or a contraindication to contrast-enhanced MRI
Study Product(s), Dose, Route, Regimen	Radiation dose and distribution within the liver adjusted based on function and tolerance of first phase of treatment. 3/5 of treatment delivered, followed by 1 month break, followed by the remaining 2/5 of treatment, with dose and spatial distribution adjusted based on biomarker and imaging tumor and normal tissue response.
Duration of Administration	3-5 treatments, depending on ICG, CP score, ALBI score and NTCP model

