5.1.2 Initial radiotherapy plan

5.1.2.1 CT with or without MRI simulation will be performed in treatment planning position, with appropriate immobilization, as is standard of care.

5.1.2.2 Radiation target volumes. The gross tumor volume (GTV) will be defined on CT or MRI. Appropriate patient-specific margins for motion will be added for patients unable to tolerate breath hold for treatment. No margin will be added for microscopic extent, as per routine clinical practice. A PTV margin will be added as per standard practice, typically 5mm radially and 8mm superiorly and inferiorly.

5.1.2.3 PTV Target Doses. Doses will be prescribed to a peripheral covering isodose covering the PTV, except in cases where this would exceed recommended doses to organs at risk (OARs). In these cases, heterogeneous dose distributions sparing these OARs are expected. The dose per fraction will be determined by the risk of liver damage, which will be fixed at $\leq 10\%$ for the initial 3/5 of treatment. The full treatment plan will be devised at this time in order to account for total normal tissue dose if patients are able to proceed with the entire treatment. The remaining 2/5 of treatment will be determined as per section 11 and potentially reduced based on liver function. Maximum prescribed tumor dose will be 55 Gy in 5 fractions, which we have shown that this dose is adequate for 95% local control at 2 years even for large tumors.

5.1.2.4 OAR Limits. Standard OAR limits in routine clinical practice will be applied and will take priority over target coverage.

5.1.3 Radiation Schedule. The first 3/5 of the treatment plan will be delivered in the initial phase. The dose of radiation will be based on baseline ICG or ALBI, CP score, and functional liver imaging for an NTCP < 10% for a predicted CP score change of greater than or equal to 2. After an approximately 4 week break and re-assessment of liver function with ICG testing or ALBI, the final 2/5 of treatment may be delivered, as per section 11. Patients who have, or would be predicted to have, unacceptable Toxicity (as defined in section 8.6) at the reassessment point will receive no additional therapy at that time.

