5.3 Duration of Therapy

Therapy would typically continue until delivery of the intended number of fractions. If liver function declines after the first 3/5 of treatments and does not recover sufficiently for additional therapy, then treatment will also be considered complete after 3 fractions (see above for definition).

Treatment will also be complete if a patient voluntarily withdraws from treatment or changes in the patient's condition render the patient unacceptable for further treatment in the judgment of the investigator.

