5.4 Off Treatment Criteria

Patients will be removed from protocol therapy when any of the criteria listed in Section 5.3 apply, with documentation provided. All patients who discontinue treatment should comply with protocol specific follow-up procedures as outlined in Section 6.3. The only exception to this requirement is when a subject withdraws consent for all study procedures, loses the ability to consent freely, or is removed from follow up per the investigator's discretion, as in Section 5.6.

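### Section 11.1 gives two different bases for withholding the last 2/5 of radiation, the MRI-enhancement stop is missing from the operational sections, and the toxicity stop cites a section that defines no toxicity

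*Combined protocol and SAP*

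**What the plan says.** Section 11.1 (Study Design) describes two ways in which the second course may be adapted globally. The first is that "if there is no remaining enhancement on the MRI scan, no further radiation will be given". The second protects patients whose livers appear sensitive to radiation. The last paragraph of 11.1 then states that "The decision to continue treating patients with further radiation is based on analysis of the information from the ICG results or ALBI", adds that RECIST measurements are not the basis, and says nothing about enhancement.

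Section 5 sends the question to section 11 twice. Section 5.1.2.3 says "The remaining 2/5 of treatment will be determined as per section 11 and potentially reduced based on liver function", and section 5.1.3 says "the final 2/5 of treatment may be delivered, as per section 11". Section 5.3 says "Therapy would typically continue until delivery of the intended number of fractions". It then names liver-function decline without sufficient recovery, voluntary withdrawal and investigator-judged unfitness as reasons why treatment is complete. Section 5.4 refers back to that list: "Patients will be removed from protocol therapy when any of the criteria listed in Section 5.3 apply". The synopsis gives the duration as "3-5 treatments, depending on ICG, CP score, ALBI score and NTCP model".

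Section 5.1.3 also withholds further therapy at reassessment for "unacceptable Toxicity (as defined in section 8.6". Section 8.6 is about reporting unanticipated problems.

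**The concern.** Whether the last two of five fractions are given is the core of the adaptive strategy being piloted. Section 11.1 says the trial should end with an approach ready for a randomized comparison, and that requires one stated rule for this decision. As written, someone following the adaptation paragraph of 11.1 and someone following its last paragraph, or section 5.3 alone, could manage the same patient differently.

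The primary analyses depend on this decision. Feasibility is a proportion of patients in whom the intended treatment was achieved, and the plan does not say how a patient who stops for lack of enhancement is scored. Tumor dose is the main covariate in the planned Cox model for local control. Under the enhancement stop, patients with a strong early imaging response receive less dose by rule. If the stop is applied unevenly and the reason is not recorded, the analysis cannot separate those patients from the ones stopped for liver function.

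**Working it through.** The plan gives no figure to reproduce on this point. The check sets the passages side by side for one test patient: the first 3/5 is complete, both liver-function assessments are done and stable, and the mid-treatment MRI shows no remaining enhancement.

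1. **What each place says for this patient.**
   - Section 11.1, adaptation paragraph: no further radiation.
   - Section 11.1, last paragraph: the decision rests on ICG or ALBI. Both are stable, so it gives no ground for stopping. It does not order five fractions either.
   - Section 11.1, dose rule: the second-course dose is the smaller of the dose that maximizes the probability of 1-year local control minus 4 times the probability of toxicity, and the dose with a 25% estimated toxicity risk. Local control is modelled on tumor dose, and toxicity includes the change in ICGR15. Enhancement is not named as an input, so the stop must come from the separate sentence.
   - Sections 5.1.2.3 and 5.1.3: refer to section 11, with permissive wording.
   - Section 5.1.4: uses the MRI to reshape dose and to aim at active tumor. It does not address the case of no active tumor.
   - Sections 5.3 and 5.4: none of the listed reasons applies.
   - Synopsis: the duration line omits MRI. The regimen line allows adjustment on imaging tumor response, which is compatible with the stop.
   - Events table, footnote 4: a patient who does not initially qualify for the final phase has a repeat IC-Green about 4 weeks later. That fits a liver-function stop but not an enhancement stop.

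2. **Size for one patient (illustration).** Section 5.1.2.3 gives a maximum of 55 Gy in 5 fractions. Assuming equal fractions, 55 / 5 = 11 Gy each. Stopping after three gives 3 × 11 = 33 Gy and completing five gives 55 Gy, a difference of 22 Gy. This is an upper bound, because the second course may be reduced.

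3. **The toxicity stop.** The reference in 5.1.3 leads to 8.6, which defines no toxicity. The definition meant cannot be recovered from the rest of the text. Section 8.7 equates unacceptable toxicity with radiation induced liver disease, while 11.1 and 11.3 use a Child-Pugh rise of 2 or more within 6 months.

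4. **Evaluability.** Section 5.7 makes patients non-evaluable if they miss the required liver-function tests or the initial 3/5. The test patient has completed both. Section 11.2 requires the complete prescribed treatment and names liver-function and toxicity stops as included, but not an enhancement stop.

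5. **Feasibility.** Section 2.3.1.1 asks for successful completion with perfusion MR used in planning. Section 11.3 asks for the full treatment with every adaptation, and singles out perfusion-based replanning. The test patient received an adaptation named in 11.1 but has no second course to replan, so either score can be argued. With 80 patients in the denominator, each such patient is worth 1/80 = 1.25 percentage points. The documents do not say how many there would be; arithmetically it lies between 0 and 80.

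**The case against.** The strongest reply is that the documents, read together, already have an order of precedence. A reader might infer that section 5 contradicts section 11.1, but it does not. It hands the last 2/5 to section 11 twice, section 5.3 describes only what typically happens, and neither 5.3 nor 5.4 calls its list exclusive. That part of the reply stands, and the fault in section 5 is omission. It does not settle the matter, because the deferral leads to the section whose own two statements differ.

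The second reply is that the last paragraph of 11.1 is there to explain why RECIST measurements are not needed, and was not meant to withdraw the enhancement rule. That is probably the intent. Even so, the sentence says positively what the decision rests on, and enhancement is not included.

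The third reply concerns the endpoints. A reader might infer that a patient stopped for no enhancement would be lost as non-evaluable. Section 5.7 points the other way, and the parenthesis in 11.2 reads as a list of examples, so that risk is weak. Scoring such a patient as a feasibility failure is also not the natural reading, since 11.1 calls the stop an adaptation and 11.3 looks at each failure individually. What remains is that the scoring is not stated.

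Finally, the wrong reference to 8.6 concerns the toxicity stop and not enhancement. It is a separate defect in the same decision and is not evidence for the first one.

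**Conclusion.** The point holds in a limited form. Section 11.1 states two bases for the decision on the last 2/5 that do not agree as worded. The enhancement stop is missing from 5.3 and 5.4, the synopsis duration line and footnote 4. The toxicity criterion in 5.1.3 has no definition where the text sends the reader.

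The documents do not support saying that section 5 orders five fractions for a patient without enhancement, or that a given share of the feasibility proportion is at risk. No proportion without enhancement is stated, so only the per-patient values can be given: up to 22 Gy, assuming equal fractions at the maximum prescription, and 1.25 percentage points of feasibility, assuming a denominator of 80.

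Severity is moderate. These are stated rules that need correcting, and they govern the intervention and a primary endpoint. However, the likely intent can largely be read from the text, and the trial is a single-arm pilot.

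**What to change.** - Reconcile the adaptation paragraph and the last paragraph of 11.1 so that the bases for giving or withholding the last 2/5 are stated once. Which clinical rule applies is for the investigators to decide.
- Carry the reconciled rule into 5.1.3, 5.3 (and so 5.4), the synopsis duration line and footnote 4 of the events table.
- In 5.1.3, replace the reference to 8.6 with the definition of unacceptable toxicity that is intended.
- Record for each patient the reason treatment ended.
- In 2.3.1.1, 11.2 and 11.3, state how a patient stopped under a protocol-specified adaptation (liver function, or no enhancement if that rule is kept) counts for evaluability and for feasibility. Do not count voluntary withdrawal or investigator-judged unfitness as feasible merely because 5.3 lists them. That would inflate the proportion.

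The cost is a protocol clarification and one case report form field. The sample size and the planned models do not change.
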